6.4 SUBJECT SETS ANALYSED

The subject sets will be used as defined in the CTP, Section 7.2.1. These include the Enrolled set (ES), Randomised set (RS), Treated set (TS) and Full analysis set (FAS).

- Screened set (SCR) – this analysis set includes all patients having signed informed consent. The SCR will be used for analyses of patient disposition.

- 
- 
- 

The discussion on all exceptional cases and problems and the decisions on the allocation of patients to populations will be made at latest at the DBLM.

In Table 6.4:1 the subject sets which are to be used for each class of endpoint are illustrated.

Table 6.4: 1 Subject sets analysed

Class of endpoint	Subject set			
	SCR	RS	TS	FAS
Disposition	X			
Primary endpoint			X	
Secondary efficacy and [REDACTED]			X	
Secondary and further safety endpoints (including liver decompensation) & treatment exposure		X		
Demographic/baseline endpoints	X			
[REDACTED]				

Handling of Treatment Misallocations in Analysis Sets

[figure not shown]
If a patient was administered incorrect treatment during the study, for efficacy analyses:

- Subjects who took incorrect treatment will be reported under their randomised treatment group. In the case of stratification error at randomisation, the subjects will be analysed according to the stratum to which they actually belong (regardless of any mis-assignment to treatment based on identification of the wrong stratum from IRT), as such an error occurs before randomization and is therefore consistent with regulatory guidance.

Then, for safety analyses, the following will be used in addition:

- If a patient is planned to receive avenciguat (i.e., randomised to either avenciguat 2 mg BID or avenciguat 3 mg BID), then patients will be reported under the planned treatment from the randomization visit for safety analyses because the overall safety profile is expected to be driven by the amount of drug received in totality over the entire treatment duration. It is not expected that the safety profile will deviate from the planned treatment regimen if the subject receives only one or two kits of the incorrect medication at only some dosing occasions.
- If a patient is planned to receive Placebo, then patients will be reported under their randomised treatment group for safety analysis if the patient was administered no

avenciguat kits at any visit. If the patient was administered at least one kit of avenciguat during the treatment period, then the patient will be assigned to a relevant avenciguat dose treatment group (either avenciguat [REDACTED] BID or avenciguat [REDACTED] BID, depending on the kit administered).

6.6 HANDLING OF MISSING DATA AND OUTLIERS

6.6.1 Efficacy data

No imputation of missing data is planned for the efficacy endpoints.

6.6.2 Safety data

Missing safety data will not be imputed.

6.6.3 Missing dates and times

Missing or incomplete AE dates are imputed according to Boehringer Ingelheim standards (2).

If the date of first drug administration is missing but the patient was randomized, the date of the first drug administration will be set to the date of randomization. If the date of first administration is partially missing with the month and year present, the day will be set to the date of randomization if randomisation was in the same month. If randomization was in the month prior to the first drug administration the missing day will be imputed as the first day of the month.

Partial start and stop dates for concomitant therapies will be imputed to enable subsequent calculation (but not for display) by the following “worst case” approach:

- If the day of the end date is missing, then the end date is set to last day of the month (or to the patient’s trial completion date, whichever is earlier).
- If the day and month of the end date are missing, then the end date is set to 31st of December of the year (or to the patient’s trial completion date if it is earlier than 31st December of the year).
- If the day of the start date is missing, then the start date is set to first day of the month.
- If the day and month of the start date are missing, then the start date is set to 1st January of the year.

All other cases need to be assessed by the trial team on an individual basis, using above points as guidance.

6.6.6 Time since first diagnosis

For incomplete information on the date of the first diagnosis of cirrhosis, time since first diagnosis will be calculated as follows:

- If the year of first diagnosis is unknown, then the time since diagnosis will be set to missing.
- If day and month of the first diagnosis are unknown, time since first diagnosis will be calculated as if diagnosed on the 30th June of that year.
- If only the day of the first diagnosis is unknown, time since diagnosis will be calculated as if diagnosed on the 15th of that month.

6.7 BASELINE, TIME WINDOWS, AND CALCULATED VISITS

Regarding efficacy and safety endpoints, the term “baseline” refers to the last observed measurement prior to administration of any randomized study medication.

Measurements taken prior to the first intake of randomized study medication will be considered pre-treatment values. Pre-treatment values will be assigned to a visit according to the nominal visit number as recorded on the eCRF or as provided by the laboratory.

In general, the date of the first drug administration will be used to separate pre-treatment from on-treatment values. Measurements taken after first trial medication intake will be considered on-treatment values if they have been obtained up to end of the parameter-specific follow-up period as defined in Table [6.1:1](#) below and will be assigned to the randomized study medication for efficacy analyses and to the first study medication taken for safety analyses.

Measurements taken after the end of the endpoint specific follow-up period will be considered post-treatment values.

Table 6.7:1 Endpoint specific follow-up period for the assignment to treatment phase

Endpoint	Last day of assignment to treatment phase (Days after study medication stop date)
Efficacy	
HVPG	8
[REDACTED]	
Safety	
Adverse events	7
Safety laboratory measurements	3
Vital signs (including body weight, blood pressure)	1

For derivation of the last value on treatment, minimum value on treatment, and maximum value on treatment, all values from the relevant phase (whether or not collected in any time window; see Table [6.1:1](#) for definition of the trial phases) will be considered; these will be derived for analysis of laboratory and vital signs data.

On-treatment efficacy, safety [REDACTED] measurements will be assigned to visits based on the extended time windows around the planned visit dates, defined relative to the day of first trial medication intake (see Table [6.7:2](#)).

For the analyses of the secondary and further safety endpoints at week 8, the actual V7 date + X days (X=3 or 7 days for safety laboratory and AE respectively) will be used for the analysis time windows.

Table 6.7:2 Time windows for assignment of measurements to visits for statistical analysis

Visit number /name	Visit label	Planned day	Time window (Days)				
			Window (per CTP)	Start (per CTP)	End (per CTP)	Start (extended) *	End ^A (extended) *
V1	Screening	-42	+7			-∞	0
On-treatment							
V2	Week 0	Day 1	N/A	1	1	≤1	1
V3	Week 1	Day 8	+2	8	10	2	11
V4	Week 2	Day 15	[contact]
V5	Week 4	Day 29	[contact]
V6	Week 6	Day 43	±3	40	46	37	50
V7	Week 8	Day 57	±3	54	60	51	71
V8	Week 12	Day 85	±5	80	90	72	99
V9	Week 16	Day 113	±5	108	118	100	127
V10	Week 20	Day 141	±5	136	146	128	155
V11	Week 24/ EoT	Day 169	±5	164	174	156	Study medication stop date + X [#] days
Off-treatment							
V12	Week 28/ EoS	Day 197	±5	192	202	Study medication stop date + X [#] days	Day of last follow-up value days +1

^A In case of premature discontinuation of the study medication, an early EoT visit has to be performed within 7 days of medication stop date. If such an EoT Visit falls into the time window of a previous visit, measurements will be assigned to this previous visit and the visit value will be determined as described above. In this case, the time window for the visit that includes the early EoT visit will end X days after the study medication stop date, including Day X. Patients will then be asked to continue in the study according to the visit schedule. Off-treatment measurements will be assigned to visits in the same manner.

Days are counted relative to the day of first treatment, which is defined as Day 1.

* Start (extended): End of extended window of last visit+1

End (extended): Midpoint of planned days between current visit and next visit

#X= 3 days for safety laboratory; X=1 day for biomarkers and vital sign, respectively; X= 8 days for HVPG and Fibroscan data.

The midpoint between two on-treatment visits defines the end of a time window, with the midpoint being included in the time window of the preceding visit. The end of the time window of the last on-treatment visit (end of treatment (EoT)) is endpoint dependent (Table 6.7:1).

Repeated and unscheduled efficacy and safety measurements will be assigned to the nominal visits and listed in the subject data listing according to the time windows described above. Only one observation per time window will be selected for analysis at an on-treatment visit - the value which is closest to the protocol planned visit day will be selected. If there are two observations which have the same difference in days to the planned day, the first value will be selected. If there are two observations on the same day, the first value will be selected. If there

are multiple values within the time window of the last visit, including a value on the last day of drug intake, the value on the last day of drug intake is used as the value of the last visit.

Data prior to randomization will be based on nominal visits and time windowing will not be applied. For these time points, data from the scheduled visit will always be selected if they are collected correctly. Unscheduled visits will only be considered if no correct data from the scheduled visit is available. If no correct data from a scheduled visit is available and multiple unscheduled correct values are available for a visit, the first correct value will be selected.

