The combination of BI 685509 with other compounds involved in the NO-sGC-cGMP pathway, such as NO-donors (e.g. nitrates), phosphodiesterase (PDE)-5- inhibitors, non-specific PDE inhibitors and sGC-simulators might further increase the risk for hypotensive episodes and potentially reactive HR increases and the severity of these effects. Based on *in-vitro* data, BI 685509 is a weak inactivator of CYP3A4 and CYP2C8. A Drug-Drug Interaction (DDI) potential with CYP3A4 substrates cannot be excluded as BI 685509 is predicted to be a weak CYP3A4 inactivator. DDI threshold dose for CYP2C8 inactivation for the CSPH indication is close to the clinically relevant dose tested in Phase II. Thus, in addition to close monitoring of AEs among patients taking CYP3A4 narrow therapeutic index / or sensitive substrates, CYP2C8 and CYP3A4 narrow therapeutic index / or sensitive substrates will also be monitored to support patient safety. Inhibitors or inducers of UGT (uridine glucuronyl transferase) enzymes (especially UGT1A1) may potentially impact BI 685509 exposures in a clinically relevant manner. BI 685509 is a substrate of P-gp (permeability glycoprotein) and OATP (organic anion transporting polypeptide)1B1/3 transporters. Co-administration of single doses of BI 685509 and the P-gp inhibitor itraconazole increased BI 685509 C_{max} approximately 1.35-fold and AUC_{0-tz} approximately 1.55-fold, which is considered not clinically relevant. OATP1B1/3 inhibition by rifampicin increased the exposure of BI 685509 after co-administration of single doses approximately 2.15-fold for C_{max} and 2.74-fold for AUC_{0-tz}, which is considered clinically relevant. Thus, OATP1B1/3 inhibitors will be restricted (refer to Table [1.4.2: 1](#) and Section [4.2.2.1](#)).

Residual Effect Period

The Residual Effect Period (REP) of BI 685509 is 7 days. This is the period after the last dose with measurable drug levels and / or pharmacodynamic (PD) effects still likely to be present.

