1.2.3 Data from clinical studies

BI 685509 has been tested in a single rising dose trial, a food effect and DDI trial, two multiple rising dose (MRD) trials in male healthy volunteers, and one multiple oral rising dose trial in patients with DN. Overall, it was well tolerated except for dose limiting orthostatic dysregulation. In the single dose trials, BI 685509 appears to reduce diastolic and systolic BP with a compensatory increase in HR, however, up-titration and *TID* dosing markedly improved the cardiovascular tolerability of the drug.

Trial 1366-0020, an MRD trial involving hepatically impaired patients, was ongoing during Clinical Trial Protocol (CTP) writing. An interim analysis was performed.

Summary of interim analysis data from Trial 1366-0020:

In the trial, 49 patients with hepatic impairment due to various underlying liver diseases were treated for up to 4 weeks (24 patients with cirrhosis Child-Turcotte-Pugh A and 25 patients with cirrhosis Child-Turcotte-Pugh B in patients with hepatic impairment, as these are the intended patient population).

The treatment with BI 685509 in patients with cirrhosis of different aetiologies, with hepatic impairment with Child-Turcotte-Pugh A and B was safe and well-tolerated. All AEs were of mild or moderate intensity. No treatment-related SAEs, as defined by the Investigator,

occurred, or led to treatment discontinuation. Orthostatic intolerance occurred in the higher dose groups, and did not lead to treatment discontinuation, but recovered during continued treatment. Treatment with BI 685509 had no effect on laboratory parameters, including liver enzymes and bilirubin.

The exposure was comparable between Child-Turcotte-Pugh A and B patients, and no differences were seen for the different underlying liver aetiologies. Exposure of [REDACTED] *BID* in hepatic impaired patients were similar to [REDACTED] *TID* exposures observed in healthy volunteers (Trial 1366-0003) and chronic kidney disease patients (Trial 1366-0004).

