2.1.3 Secondary endpoints

Secondary endpoints include:

- percentage change in HVPG from baseline (measured in mmHg) after 8 weeks of treatment
- response defined as > 10% reduction from baseline HVPG (measured in mmHg) after 8 weeks of treatment
- response defined as > 10% reduction from baseline HVPG (measured in mmHg) after 24 weeks of treatment
- occurrence of one or more decompensation events (i.e. ascites, VH, and / or overt HE) during the 24 week treatment period
- occurrence of CTCAE grade 3 (or higher) hypotension or syncope based on Investigator judgement, during the first 8 weeks of the treatment period
- occurrence of CTCAE grade 3 (or higher) hypotension or syncope based on Investigator judgement, during the 24 week treatment period
- occurrence of discontinuation due to hypotension or syncope during the first 8 weeks of the treatment period
- occurrence of discontinuation due to hypotension or syncope during the 24 week treatment period

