4.1.4 Drug assignment and administration of doses for each patient

Trial medication will be dispensed at the investigational sites in accordance with the [Flow Chart](#). At dispensing visits patients will be given the appropriate number of medication kits (range 1-4) depending on the interval between the visits (for further kit details refer to Section [4.1.6](#)). The last dose of trial medication will be administered in the evening of the day before the EoT visit.

All patients, regardless of the treatment group they are assigned to, will start at Visit 2 on a dose of ■■■■ BI 685509 BID or matching placebo. At Visit 3, 7 days later, and again at Visit 4, a further 7 days after Visit 3, all patients will either be up-titrated or pseudo up-titrated first to a dose of ■■■■ BI 685509 BID or matching placebo, and then to a dose of ■■■■ BI 685509 BID or matching placebo. Pseudo up-titration will be used at a visit instead of a true up-titration when the maximum planned maintenance dose for a treatment group has been reached; in this way the blind across treatment groups will be maintained (refer to Table [4.1.4: 1](#)). Patients will be informed about the dose titration period and will be made aware that up-titration or pseudo-titration is being used. If a patient does not tolerate an up-titration, e.g. due to orthostatic dysregulation, the rules in Section [4.1.4.1](#) must be followed. From Visit 4 onwards, patients will continue to receive the maximum planned maintenance dose for the treatment group they are assigned to (unless a down-titration is required), until reaching the EoT visit 24 weeks after starting the trial medication.

If a patient has an AE that, based on Investigator judgement, may be related to trial medication, the trial medication can either be:

- interrupted (i.e. the trial medication is stopped, and subsequently re-started by following the up-titration approach described above)

OR

- the dose can be reduced (down-titrated) if the patient has successfully completed the dose titration period (i.e. Visit 4)

For further details refer to Sections [4.1.4.1](#) and [4.1.4.2](#).

All trial medication assignments, including up / down-titrations and provision of replacement kits, will be managed through the IRT system. Down-titrations must not be performed by instructing the patient to take less than the two daily doses (refer to Section [4.1.4.1](#)).

Table 4.1.4: 1 Drug assignment and dosage by treatment group

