7.8.1.1 Assignment of AEs to treatment

In general, the analysis of AEs will be based on the concept of treatment emergent AEs. That means that all AEs occurring between first drug intake until 7 days (residual effect period – REP) after last drug intake will be assigned to the on-treatment period. All AEs occurring before first drug intake will be assigned to ‘screening’ and all AEs occurring after last drug intake + REP of 7 days will be assigned to ‘follow-up’ (for listings only). For details on the treatment definition, see Section [6.1](#).

If only the start date of an AE is collected (without the start time), any AE occurrence on the same day as the first avenciguat administration will be assigned to the on-treatment phase.

Drug-related AEs which will be presented as actual treatment taken at each given timepoint. AEs and serious adverse events (SAEs) assigned to the following phases: screening, each treatment group (placebo, avenciguat 2 mg and avenciguat 3 mg), post-treatment for each treatment group will be listed.

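### The SAP counts adverse events up to seven days after the week-8 visit as first-8-weeks events, although patients are still taking trial medication

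*SAP*

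**What the plan says.** Protocol 2.1.3 lists "occurrence of CTCAE grade 3 (or higher) hypotension or syncope based on Investigator judgement, during the first 8 weeks of the treatment period" and "occurrence of discontinuation due to hypotension or syncope during the first 8 weeks of the treatment period". SAP 5.2.2 repeats both with the same period and adds no days.

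SAP 6.7 then states where the window closes when these and the other week-8 safety endpoints are analysed: "the actual V7 date + X days (X=3 or 7 days for safety laboratory and AE respectively) will be used". The adverse event window therefore closes seven days after the visit.

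The seven days have a defined meaning elsewhere. Protocol 1.2.1 gives a residual effect period of 7 days and explains: "This is the period after the last dose with measurable drug levels". SAP Table 6.7:1 counts the same 7 days from the stop of study medication. SAP 7.8.1.1 applies them that way too: events up to 7 days "after last drug intake will be assigned to the on-treatment period".

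V7 is not a stop of medication. The Flow Chart has drug dispensed at V7, and Protocol 4.1.4 keeps patients on their maintenance dose "until reaching the EoT visit 24 weeks after starting the trial medication". SAP section 4 declares no change from the protocol's methods.

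On the secondary point, Protocol 2.1.3 and SAP 5.2.2 limit the decompensation endpoint to ascites, variceal haemorrhage and overt hepatic encephalopathy. Under variceal haemorrhage, SAP Table 7.5.2:1 lists two whole high-level terms (*Gastric and oesophageal haemorrhages* and *Non-site-specific gastrointestinal haemorrhages*) and the preferred term *Oesophageal haemorrhage*. It also has an *Other* category.

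**The concern.** An allowance meant for patients who have stopped the drug is attached to a visit in the middle of treatment. For a patient still dosing, the week after V7 is ordinary treatment time, not a residual-effect week. Followed exactly, the rule counts an event in week 9 as one in the first 8 weeks. The cut-off also moves with each patient's actual visit date. No cut-off is stated for a patient who is still on drug but has no V7.

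These endpoints were chosen because of the drug's mechanism (Protocol 3.2), and SAP 7.8.1.3 gives adverse events that are secondary endpoints their own tables. Readers will take the 8-week label literally. In an arm of 26, one patient is 1/26 = 3.8 percentage points.

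The bleeding terms raise the same kind of problem: an event that is not variceal could be reported as variceal haemorrhage and so count as decompensation.

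**Working it through.** **Inputs.** Day 1 is first dose (SAP Table 6.7:2 footnote: "Days are counted relative to the day of first treatment, which is defined as Day 1"). V7 is planned for week 8 with a window of ±3 days. There are 26 patients per arm (Protocol 7.5). The documents give no event rates for these endpoints, so the 8-week risks below are assumptions.

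**Reproducing the SAP's days.** V7 = 8 × 7 + 1 = Day 57. The protocol window is 57 ± 3 = Days 54 to 60. The extended window runs from the midpoint of 43 and 57, plus 1, = Day 51, to the midpoint of 57 and 85 = Day 71. All agree with Table 6.7:2.

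**Cut-off under the SAP rule (actual V7 day + 7).** Eight full weeks end on Day 56.

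| Actual V7 | Cut-off | Days beyond V7 | Days beyond Day 56 |
|---|---|---|---|
| Day 54 | Day 61 | 7 | 5 |
| Day 57 | Day 64 | 7 | 8 |
| Day 60 | Day 67 | 7 | 11 |

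Week 9 is Days 57 to 63, so a V7 on its planned day brings in the whole of that week.

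**Expected extra patients, constant hazard.** With 8-week risk p, the event-free probability is S(t) = (1 − p)^(t/56). The probability of a first event in the seven added days is d = S(57) − S(64). Extra patients per arm = 26 × d. The chance of at least one extra patient in an arm = 1 − (1 − d)^26.

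| Assumed p | d | Extra patients per arm | Chance of at least one |
|---|---|---|---|
| 2% | 0.25% | 0.064 | 6.2% |
| 5% | 0.61% | 0.158 | 14.6% |
| 10% | 1.18% | 0.306 | 26.5% |

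Putting V7 on Day 54 or Day 60 changes the expected count by less than 0.002 patients.

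**Expected extra patients, events clustered in titration.** Assume 80% of the 8-week cumulative hazard falls in Days 1 to 28, and the other 20% is spread over Days 29 to 56 and continues at that rate. The extra patients per arm are then 0.026, 0.063 and 0.123, and the chances of at least one are 2.5%, 6.1% and 11.6%.

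**Bleeding terms.** No arithmetic applies, because the documents give no bleeding rates. The comparison is by name. The endpoint says variceal; the two high-level terms name a site or no site; *Oesophageal haemorrhage* names a site. None of the three names a variceal source.

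**The case against.** The V7 + 7 rule is stated openly and mirrors the last-dose + 7 allowance used for adverse events in general. The added events are real on-treatment events, and the 24-week versions of the same endpoints count them anyway. Nothing is lost or invented; only the boundary between week 8 and week 9 moves. The rule is the same in every arm, and Protocol 7.1 plans no testing. All of this stands and limits the weight of the point. It does not make the label right for patients who are still dosing.

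A reader might infer that the safety comparison between arms, or the primary result on hepatic venous pressure gradient, is biased. The documents do not support that: the rule does not depend on arm, and the primary analysis does not use this window.

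A reader might also try to bound the event risk from the interim data in Protocol 1.2.3, where 49 patients were treated for up to 4 weeks and "All AEs were of mild or moderate intensity". That section does not say how many received active drug, and it reports placebo-corrected results from the same trial, so no reliable upper limit follows.

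On bleeding, a broad search is defensible. Enrolled patients have documented or previously treated varices, and a variceal bleed may be coded non-specifically. No gastroscopy is scheduled after screening, so demanding proof of variceal origin would drop some true cases. Nor is it right to infer that bleeds go unreviewed: a decompensation event is an intercurrent event, and SAP 6.3 has these confirmed by medical review before database lock. What is missing is a link from that review to the endpoint count.

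**Conclusion.** The 8-week window is wrong as written, and minor. That the cut-off lies seven days past V7 follows from the text alone. The size, about 0.03 to 0.31 extra patients per arm, rests on assumed 8-week risks of 2% to 10% and on the two hazard shapes shown. The harm is limited to descriptive counts that do not match their label.

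The bleeding terms are a secondary labelling point. The mismatch is clear by name, but its effect cannot be computed, and the documents do not support narrowing the count to proven variceal bleeds only. Whether the *Other* category counts towards the endpoint is left unsaid.

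**What to change.** **SAP 6.7, week-8 safety endpoints.**
- For patients still on drug, end the window at one stated day, planned V7 (Day 57), without the added seven days. Day 56 is an equivalent convention; what matters is that one day is fixed. This also covers a patient still on drug who misses V7.
- For patients who stopped earlier, use last dose + 7 days, capped at the same day.
- Date the grade 3 or higher endpoint by adverse event onset, and the discontinuation endpoint by the date of discontinuation.

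**SAP Table 7.5.2:1.**
- Keep the broad search.
- Show explicitly variceal or medically confirmed bleeds in one row, and the remaining upper gastrointestinal or non-specific bleeds (including unconfirmed *Oesophageal haemorrhage*) in a second, correctly labelled row.
- Give the endpoint count both with and without the second row, so that unconfirmed variceal bleeds stay visible.
- Link the SAP 6.3 medical review to this classification.
- State that *Other* is outside the endpoint count.

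**Cost.** SAP wording, some programming, and a small addition to the review already planned before lock. With a Day 57 cut-off and V7 held on Day 58 to 60, events between the cut-off and the visit leave the 8-week count but stay in the 24-week count. Some bleeds will remain unconfirmed, because confirmation depends on unscheduled source data.
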